Each patient's GFR will be recorded prior to the exams and 48-72 hours after scanning. In addition, each patient will be contacted at baseline as well as 6 weeks, 3 months, and 6 months post-scan to comprehensively evaluate for any symptoms or signs of NSF (see attached sheet) [19]. If at any point a patient's follow-up interviews indicate they might be experiencing symptoms of NSF, or if their post-MRI research blood draw indicates deteriorating renal function, the study PI will be notified and the patient will be referred for further medical evaluation, if necessary. All relevant demographics, such as hypertension, diabetes, coronary artery disease, and liver disease, will be recorded. The data will be analyzed, using standard statistical methods, for any significant and disparate variations in renal function.

Aim 2:

Each MRI exam will be independently interpreted by 2 participating sub-specialty-trained (either neuro or body) radiologists. To limit bias, the readers will initially be blinded to history and prior exams and their respective interpretations recorded in the research database (history and prior exams will subsequently be provided, as usual, for the final interpretations used in clinical care). The interpretations and inter-reader correlation will be recorded for each exam. Via Loyola electronic medical record (EMR) we will record the chronology of all subsequent related diagnoses, imaging studies, pathology results, therapies, and related costs (defined as gross hospital charge), within the study period (1-2 years) and for one year afterward. These data will be analyzed to compare differential outcomes between the non-contrast and contrast cohorts.

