To further explore the concept of Gadoterate-based differential outcomes, two separate interpretations for each Gadoterate-enhanced MRI will be recorded in the research database: an interpretation based upon only the non-contrast images and the full interpretation of the whole exam (non-contrast + contrast images). We will subsequently record the *predicted* outcome data, as described above (diagnoses, subsequent imaging studies, pathology results, therapies, and projected related costs), that would be associated with the more limited interpretation of the non-contrast images. Comparison to the actual outcomes of that patient will subsequently be analyzed. This is both feasible and straightforward since the vast majority of the clinical MRI indications in this study have a well-defined diagnostic/therapeutic pathway – i.e. a solitary liver lesion demonstrated to be malignant by contrast MRI would result in chemo-embolization, whereas an indeterminate result based on non-contrast would lead to a liver biopsy [18]. Another example: Cystic renal lesions which cannot be completely characterized without contrast are typically followed with serial imaging exams to check for growth, whereas demonstration of a simple cyst by contrast-enhanced exam will typically result in no further imaging.

Statistics:

Previously-tested GBCAs in chronic kidney failure patients have resulted in 10-25% rates of decreased GFR, depending upon the study, with most investigations recording rates in the range of ~15% [5]. Based upon various data thus far (noted above), the rate is expected to be no more than 5% using Gadoterate;

therefore if we wish to detect a significantly lower rate of renal complications with a power of 90% and a 5% significance, then a sample size of approximately 136 patients receiving Gadoterate is properly powered to address Aim 1. The non-Gadoterate control arm does not need to be as large for analysis of Aim 1, however, it will consist of 136 patients as well, to properly power analysis of Aim 2. This number is expected to be more than sufficient considering that significant interpretive and outcome differentials are anticipated at a far greater rate than 5%, between the non-contrast image and contrast image evaluations.

Study Procedures

Subject selection

Inclusion Criteria: GFR less than 30 ml/min, but not on dialysis, with indications for MRI as described above. GFR will be calculated in the same fashion as in current use in our department:

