Gadoterate will be the only contrast agent used. There is no placebo and no blinding is needed. Gadoterate will be provided by Guerbet pharmaceuticals and will be stored in the identical fashion that all Gadolinium agents are stored in the department (see attached package insert). Gadoterate will be administered according to its standard weight-based protocol, 0.2 mL/kg [8].

Administrative Organization

This will be a single site study conducted at Loyola University Medical Center. Patient recruitment and participation from the referring clinicians in the hepatology, neurosurgery, neurology, neurosurgery, and urology divisions will be coordinated by an MRI nurse coordinator, who will devote 10% time to this project. In addition, all blood draws and patient follow up will be coordinated by the nurse coordinator. All imaging will be conducted on-site. The standard LUMC laboratory locations and procedures will be used to calculate GFR from the patients' serum.

The clinical research office (CRO) will assist with statistical data analysis.

Safety and Monitoring

As with any intravenous contrast agent, numerous nonspecific adverse (mostly allergic-type) reactions are possible, though rare (see attached package insert), for Gadoterate, and no more common than in any other agent in clinical use. The most serious adverse event is difficulty breathing. Patient safety related to

such events will be monitored by direct technician and nurse supervision at the time of the exam and in the immediate period following – this is standard department protocol for all contrast MRI exams.

The main additional serious adverse reaction is the one being specifically monitored in this study - renal toxicity. Monitoring of this will be done by 48-72 hour post-exam serum creatinine evaluation, as described above. In addition, long-term toxicity in the form of NSF will be evaluated by detailed phone follow-up, designed to identify any potential signs of NSF (see Figure 2). In the event of a positive response to 3 or more of the questions in the questionnaire, the patient will be assisted in scheduling a Dermatology appointment at LUMC.

The PI ([name]) and the nurse coordinator will be responsible for tracking and assessing any adverse events.

Reporting of Adverse Events or Unanticipated Problems involving Risk to Participants or Others:

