Any adverse events, as described above or unanticipated, involving risk to participants, will be promptly submitted to the IRB in accordance with established guidelines.

In addition, all data related to renal function and NSF will be routinely reviewed by the PI every 3 months.

Analysis

Image analysis: As described above, each MRI exam will be independently interpreted by 2 participating sub-specialty-trained (either neuro or body) radiologists, with the readers blinded to history and prior exams. For both contrast and non-contrast exams, the images will be viewed in the standard clinical fashion (Intellispace PACS system). For the contrast exams, the interpreting radiologists will first render an evaluation based upon *only* the non-contrast images - these interpretations will be recorded only within the research database. As described earlier, this will enable evaluation of the added advantages of the contrast agent. The overall contrast-exam interpretations, as well as the interpretations of the non-contrast exams, will be recorded in both the research database as well as dictated into the EMR, since these studies will be ordered as part of clinical care. The CRO will assist in analyzing trends of inter-reader correlation and variability.

Outcomes analysis: We will analyze the differential outcomes, between the two cohorts, as well as between the projected and actual outcomes within the contrast cohort, in these specific categories: diagnoses, number and types of subsequent imaging studies, pathology results, therapies, and related costs (defined as gross hospital charge), within the study period and extending 1 year afterward. The CRO will assist in analyzing variation within these metrics between the non-contrast vs. contrast cohorts. The CRO will also assist in analysis of variation between the projected outcomes and actual outcomes within the contrast cohort.

Risks vs Benefits

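### In the contrast cohort, the non-contrast read is not masked and the predicted pathway has no fixed time point, so the within-cohort comparisons are open to bias

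*Combined protocol and SAP*

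**What the plan says.** The reading procedure is described in two places: Study Design, Aim 2, and Analysis, Image analysis.

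- **Readers and masking.** Two subspecialty radiologists read each exam independently. Aim 2 says: "To limit bias, the readers will initially be blinded to history and prior exams". These initial reads go into the research database, and the withheld information is then supplied for the clinical read. Image analysis repeats the masking as "with the readers blinded to history and prior exams".
- **Two reads per contrast exam.** Aim 2 says that "two separate interpretations for each Gadoterate-enhanced MRI will be recorded in the research database", namely "an interpretation based upon only the non-contrast images and the full interpretation of the whole exam".
- **Order.** Image analysis says that for contrast exams "the interpreting radiologists will first render an evaluation based upon" the non-contrast images only. Of these it adds: "these interpretations will be recorded only within the research database".
- **Display.** For both kinds of exam, "the images will be viewed in the standard clinical fashion (Intellispace PACS system".
- **Predicted pathway.** Aim 2 says that the team will afterwards record the diagnoses, further imaging, treatment and costs that the non-contrast read would have led to. These are then compared with what happened to the same patient. Outcomes analysis lists this next to a separate comparison of the two cohorts.

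**The concern.** Hypothesis 2 holds that contrast gives more definitive readings and better care. Whether a read is definitive is a judgement by the reader. Here the reader making the non-contrast judgement can be expected to know that contrast images of the same patient come next, and that nothing clinical rests on the answer. Expectation, or simply the ease of deferring, can then move reads towards indeterminate.

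Such a shift feeds into the outcome. Aim 2's own liver example takes an indeterminate non-contrast result to biopsy, and its renal example takes an incompletely characterised cyst to repeated imaging. An extra deferral can therefore become a projected procedure that contrast appears to have avoided.

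The second gap is timing. EMR outcomes are followed through the study period and for one year afterwards. A projected pathway written down when the contrast findings or the real course are already visible is open to hindsight.

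The within-cohort comparison deserves protection because each patient is their own control. The two cohorts, by contrast, are largely self-selected: under Selection, eligible patients who decline Gadoterate are asked to form the non-contrast arm.

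**Working it through.** **1. What the text provides for**

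| Safeguard | In the plan? |
|---|---|
| Non-contrast read before contrast read | Yes (Image analysis) |
| Two independent readers | Yes (Aim 2; Image analysis) |
| Masking to history and earlier scans | Yes, initially (both sections) |
| Masking to cohort or to the coming contrast series | Not described |
| Contrast series hidden in the viewer | Not described; standard clinical viewing |
| Lock or time stamp on the non-contrast read | Not described |
| Criteria for indeterminate | Not described |
| Predicted pathway fixed before outcomes are known | Not described |

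That readers know contrast follows is an inference. It is a strong one: the separate non-contrast step exists only for contrast exams, the same radiologists go on to the full read, and viewing is standard.

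**2. The plan's own figure**

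Statistics gives 136 patients per cohort and says that the second 136 is there to power Aim 2. It states no indeterminate rate, no discordance rate and no test for Aim 2, only that differences are expected at well above 5%. There is no Aim 2 calculation to reproduce. I use 136 only as the number of paired exams.

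**3. Illustration of sensitivity (all rates are assumptions)**

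Suppose that contrast truly adds nothing. Paired reads of the same exam disagree by chance at rate c in each direction, and reader behaviour adds a shift d towards indeterminate on the non-contrast read.

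- Exams affected = d × 136.
- Total discordance = 2c + d, and net difference = d.
- Probability that a two-sided 5% McNemar test favours contrast (normal approximation) = Φ[(d√136 − 1.96√(2c + d)) / √(2c + d − d²)].

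Worked case, c = 0.05 and d = 0.05: (0.05 × 11.66 − 1.96 × √0.15) / √(0.15 − 0.0025) = (0.583 − 0.759) / 0.384 = −0.458, so the probability is about 0.32.

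| Shift d | Exams of 136 | Probability, c = 5% | Probability, c = 2% |
|---|---|---|---|
| 2 points | 2.7 (about 3) | 0.10 | 0.16 |
| 5 points | 6.8 (about 7) | 0.32 | 0.49 |
| 10 points | 13.6 (about 14) | 0.75 | 0.89 |
| 15 points | 20.4 (about 20) | 0.95 | 0.99 |

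With d = 0 the formula gives Φ(−1.96) = 0.025. The table treats each exam as one pair of reads, since the plan does not say how the two readers are combined. It shows that a modest shift would matter. It does not show that a shift occurs.

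**The case against.** The plan has real safeguards. It prescribes that the non-contrast read comes first, so a reader who follows it cannot carry contrast findings into that read; what is missing is an explicit lock. Two readers work independently. Aim 2 also argues that most indications have a well-defined pathway, which limits the freedom in projecting outcomes. These points stand as partial protection. None removes an expectation that both readers share, and none separates the projected pathway from the known outcome.

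Four stronger readings are tempting, and the documents do not support them.

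- **That indeterminate reads are inflated.** The documents give no rate and no evidence of a shift. A read without clinical consequence could also make some readers commit more freely.
- **That control readers must commit while contrast-cohort readers need not.** Aim 2 gives every exam an initial research read before the clinical one, so this asymmetry is not established. Clinical non-contrast reads can also be indeterminate, as the plan's own examples show.
- **That the plan rejects reader masking outright.** The sentence "There is no placebo and no blinding is needed" stands in the Gadoterate section, beside supply, storage and administration. It concerns the agent; reader masking is dealt with elsewhere.
- **That the benefit of Gadoterate is overstated in general.** The outcome comparison between cohorts does not use the contrast cohort's non-contrast reads. Aim 1 safety is untouched.

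**Conclusion.** The concern holds as a risk of bias in the paired-read and projected-versus-actual comparisons within the contrast cohort. The more plausible direction is towards Gadoterate; the size is unknown. The conclusion rests on the plan's silence about masking, locking and timing, and on the inference that readers know contrast follows.

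The 7 to 20 exams for a 5 to 15 point shift show sensitivity only. They are not a count of false biopsies or scans, because an extra indeterminate read need not change the projected pathway.

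A related limit remains. The initial research reads are made without history or earlier scans, whereas actual care follows final reads that have them. Part of any projected-versus-actual difference may therefore not be due to contrast, and the report should say so.

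The point should be acted on because the remedy is cheap and protects a useful comparison. It does not invalidate the study.

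**What to change.** For prospectively enrolled exams in both cohorts:

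1. At the initial research read, show only the non-contrast series, with any contrast series and the cohort label hidden.
2. Have each reader record the interpretation and the next step it implies, using criteria for indeterminate that are written beforehand.
3. Lock and time-stamp the entry before any contrast series, history or earlier scans are released. The clinical read then proceeds as planned.
4. Derive the predicted pathway from the locked entry alone, and fix it before EMR outcomes are opened.

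Flag controls enrolled after their MRI, which Recruitment allows within 24 hours of the scan. Their images may already have been read clinically, so the masked first step may not be possible for them.

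A comparison of indeterminate rates between cohorts should not serve as a check for reader bias. The cohorts are self-selected, so a difference could be case mix. If reported, it should be descriptive only.

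The cost is some PACS and database set-up and a slightly longer reading session. No extra patients or readers are needed.

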In reviewing the radiology informatics system, the coordinator may identify a patient who meets eligibility criteria and whose GFR has already been obtained through standard care, but who already had a standard MRI completed without contrast within the past 24 hours. If this occurs, the PI will be notified to determine if it is appropriate to contact the patient and obtain consent post-MRI. If the patient consents

to the study, they would be placed into the control (non-contrast) group and undergo the remaining study activities of post-MRI blood draw and questionnaires at baseline, 6 weeks, 3 months and 6 months.

Consent

A discussion of the study, including discussion of risks and benefits, will be conducted by the study staff (PI, sub-investigator, research nurse, or study coordinator) with the patient at least 8 hours prior to the exam (except, as noted above, in the event a patient is identified post-exam). The consent form can then be signed at the time of the exam. Consent will be obtained following our institution's policies and procedures. Patient eligibility will be confirmed prior to study enrollment.

If a patient is unable to give informed consent due to cognitive dysfunction (for example, stroke, trauma, or encephalopathy from liver failure), their guardian, spouse, parent, or the individual holding power of attorney for their healthcare will be approached to consent for the patient. If the patient regains his or her ability to make decisions, he or she will be informed about the study and asked for a decision about continued participation. In the event the patient does not regain his or her ability to make decisions at the time the questionnaires are administered, the individual who consented on behalf of the patient will be asked to answer the symptom questionnaires on the patient's behalf.

Recruitment materials

No advertising will be provided. Written material will consist of the ICD. \$25 will be provided to patients as compensation for their 2-3 day return visit (blood-draw) and \$5 for parking.

Selection

It is expected that a significant percentage of patients fulfilling the eligibility criteria will nevertheless choose to decline receiving Gadoterate and receive the default non-contrast exam. These patients will be asked to take part as the non-contrast arm of the study.

Gadoterate

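### The between-cohort Aim 2 comparison specifies no adjustment for visible disease, although a blinded non-contrast read is planned in both self-selected cohorts

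*Combined protocol and SAP*

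**What the plan says.** **Allocation.** The cohorts are not randomised. Under Selection, eligible patients who decline Gadoterate form the comparison group: "These patients will be asked to take part as the non-contrast arm of the study". Under Recruitment, patients who have already had a non-contrast MRI within the past 24 hours may also be consented into the control group.

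**Reads.** Study Design, Aim 2 has each exam read by two sub-specialty radiologists: "the readers will initially be blinded to history and prior exams and their respective interpretations recorded in the research database". For a control patient this is a read of non-contrast images. For each Gadoterate patient two interpretations are recorded: "an interpretation based upon only the non-contrast images and the full interpretation of the whole exam". Analysis, Image analysis says that the non-contrast interpretation comes first, and that "these interpretations will be recorded only within the research database".

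**Use of the reads.** In the contrast cohort the non-contrast read feeds the projected outcomes, which are compared with the same patients' actual outcomes.

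**Between-cohort analysis.** Analysis, Outcomes analysis lists diagnoses, later imaging, pathology, therapies and charges. Its only statement of method for the cohort comparison is "The CRO will assist in analyzing variation within these metrics between the non-contrast vs. contrast cohorts".

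**The concern.** Aim 2 asks whether contrast changes later care. Study Design, Aim 2 gives the causal chain itself: an indeterminate liver lesion leads to biopsy, and an uncharacterised cystic renal lesion leads to serial imaging. Disease visible before contrast is therefore prognostic for the outcomes being compared. If one cohort has more of it, imaging counts, therapies and charges will differ without any contrast effect, in either direction.

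The protocol's one argument for comparability is the note after the Exclusion Criteria. It concerns GFR decline, and it relies on pre-existing conditions being represented in both cohorts and on statistical power. Power does not remove a selection difference. Comorbidities are recorded under Aim 1 but are not linked to the Aim 2 analysis, and they do not describe the imaged lesion. A baseline measure that does describe it is already planned in both cohorts, and the between-cohort comparison makes no stated use of it.

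**Working it through.** **1. The plan's own figure.** The Statistics section expects 5% with Gadoterate ("the rate is expected to be no more than 5% using Gadoterate") against about 15% for other agents, and concludes: "power of 90% and a 5% significance, then a sample size of approximately 136 patients receiving Gadoterate is properly powered to address Aim 1". A one-sample, two-sided calculation against a fixed 15% gives (1.96 + 1.2816)² × 0.15 × 0.85 / 0.10² = 10.51 × 0.1275 / 0.01 = 134. The t version gives 135.9, so 136 is reproduced for Aim 1. The control cohort is also set at 136, for Aim 2, but no Aim 2 mean, SD or effect size is given. That use of 136 cannot be reproduced.

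**2. Is the baseline read available in both cohorts?**

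| | Control | Gadoterate |
|---|---|---|
| Non-contrast images read by two radiologists blinded to history | Yes, the exam itself | Yes, before the full read |
| Stored in the research database | Yes | Yes |
| Used in the between-cohort analysis | Not stated | Not stated |
| Used within the cohort | n/a | Yes, for projected v actual outcomes |

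One doubt remains. For controls consented after their MRI, Recruitment lists only the blood draw and questionnaires as remaining activities, whereas the Aim 2 text and Image analysis cover each exam.

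**3. Illustrative bias with no contrast effect.** Only n = 136 per cohort comes from the protocol; everything else here is assumed. Three levels of visible disease have mean follow-up studies m = 0.5, 2.5 and 4. Counts are gamma-Poisson with dispersion k = 1 to 4.

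- Mean = Σpm. Variance = Σpm + Σpm²/k + (Σpm² − mean²).
- Controls, mix 40/40/20%: mean 0.2 + 1.0 + 0.8 = 2.0; Σpm² = 5.8; variance 2.0 + 5.8/k + 1.8 = 9.6 (k = 1) or 5.25 (k = 4).
- Gadoterate, mix 30/45/25%: mean 2.275; Σpm² = 6.8875; variance 10.87 or 5.71. Mix 25/45/30%: mean 2.45; Σpm² = 7.675; variance 11.80 or 6.04.
- SE = √[(variance₁ + variance₂)/136]; z = difference/SE; false-positive rate = Φ(z − 1.96) + Φ(−z − 1.96).

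| Gadoterate mix | False difference | SE (k = 1, k = 4) | z | False-positive rate |
|---|---|---|---|---|
| 30/45/25% | 0.275 (14% of 2.0) | 0.388, 0.284 | 0.71, 0.97 | 11%, 16% |
| 25/45/30% | 0.45 (22% of 2.0) | 0.397, 0.288 | 1.13, 1.56 | 21%, 35% |

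Doubling to 272 per cohort leaves the 0.45 unchanged and multiplies z by √2, to 1.60 and 2.21. The false-positive rate rises to 36% and 60%. A larger sample makes the false finding more likely.

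**4. What adjustment recovers.** In simulation of the same scenarios, adjusting for an error-free read returns the difference to about 0 and the false-positive rate to 5–6%. That result depends on the read being the only confounder and free of error. With 20–40% of reads reassigned at random in the 25/45/30% scenario, 0.16 to 0.30 of the 0.45 remains, with an error rate of roughly 7–19%. A second set of assumptions agrees. With outcome–read correlation r = 0.5 and cohort imbalance D = 0.3 SD, the expected bias is rD = 0.15 SD. Simulation gives 0.148 SD and 22% false positives unadjusted; about 0 and 5% with a perfect read; 0.045 SD and 7% with read reliability 0.7.

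**5. Precision with identical mixes.** The adjusted/unadjusted variance ratio is (2.0 + 5.8/k)/total: 7.8/9.6 = 0.81 for k = 1 and 3.45/5.25 = 0.66 for k = 4. That is worth 136/0.8125 = 167 to 136/0.657 = 207 unadjusted patients per cohort.

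**6. Why the coding matters.** Contrast-cohort readers know that contrast images follow and may be readier to call a finding indeterminate. Suppose true mixes are identical, there is no contrast effect, and these readers move 15–40% of lowest-level cases up to the middle level (assumed). The unadjusted analysis stays near 5%. Adjusting for that grade creates a false difference of about −0.11 to −0.29 studies, with an error rate of roughly 6–19%.

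**The case against.** The strongest reply is that the protocol is silent on method and does not declare an unadjusted analysis. That stands: a reader might infer that the cohorts will be compared unadjusted, and the text does not say so. But nothing commits the analyst to adjust either, and covariates chosen after outcomes are known are a weakness in themselves.

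Second, a reader might infer that patients or ordering physicians choose contrast because of what they expect to find. The documents do not support this. They tie non-contrast ordering to GFR concerns and give no reason for declining, and the read does not exist when the choice is made. Imbalance in visible disease is possible in self-selected cohorts but is not shown. This is why the first step of the remedy is a balance table.

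Third, the comparison of projected with actual outcomes uses this read within the same patients, so between-cohort selection cannot distort it. That is a real mitigation, and Aim 2 does not rest on the cohort comparison alone. It relies on predicted outcomes, however, and does not repair the comparison of actual outcomes for which the 136 controls are justified.

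Fourth, lesion type and size do not suit the carotid and abdominopelvic vascular indications, so coding needs more than one template. This stands and is reflected in the fix.

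**Conclusion.** The point holds as a gap in specification with a cheap remedy. The cohorts are self-selected, the between-cohort analysis of later care names no adjustment, and a pre-contrast baseline that the protocol itself treats as driving later care is planned in both cohorts. Any imbalance in visible disease would be counted as a contrast effect, and sample size would not remove it.

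The figures (false differences of 0.275 to 0.45 studies, false-positive rates of 11% to 35%, variance reduction of 19% to 34%) are illustrations. The mixes, means and dispersion are all assumed, and the documents do not give the size or direction of any bias. A reader might take the near-zero adjusted result as proof that adjustment cures the problem. It does so only for an error-free read that is the sole confounder. The protocol plans to analyse inter-reader variability, and decliners may differ in ways the images do not show.

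**What to change.** In Analysis, Outcomes analysis:

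1. Tabulate objective non-contrast findings by cohort as a balance check: lesion present or absent, number, largest size, cystic or solid; for vascular exams, stenosis or aneurysm present or absent.
2. Make the between-cohort analyses of imaging counts, therapies and charges regression or stratified analyses adjusted for these findings, MRI indication and the recorded comorbidities. Show the unadjusted result alongside.
3. Do not use benign/indeterminate/suspicious or any other confidence grade as the covariate.
4. Fix the coding, and the rule for combining the two readers' findings, before outcomes are tabulated.
5. Confirm that controls consented after their MRI receive the same blinded read.
6. Do not apply the adjustment to the interpretation outcome itself, since in controls the non-contrast read essentially is that outcome.
7. State that residual confounding from read error and unmeasured selection remains.

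The cost is coding work by indication, one balance table and a few covariates. No new patients or scans are needed, and no new reads provided item 5 is confirmed.
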